**7.10.2 Laboratory Tests**

Clinical significance of laboratory findings will be evaluated by the Investigator with respect to pre-defined clinically relevant ranges taking into account the Investigator's normal ranges. The laboratory data will be listed in full with clinically relevant values flagged (L=Lower than normal range, H=Higher than normal range or A=Abnormal). A listing of laboratory values will be provided for subjects with any clinical significant findings (list relevant laboratory parameters only).

Lab parameter values and changes from baseline, except for urinalysis will be listed and summarized descriptively by cohort, group and scheduled visit.

For urinalysis, number and percentage will be presented. Shift tables will present the changes in clinically relevant categories from baseline to each scheduled post-baseline visit.

Below is a list of the laboratory tests:

Hematology	Hemoglobin, hematocrit, red blood cell count, white blood cell count, platelet count, MCH, MCHC, MCV, differential white blood count
Biochemistry	Na, K, Cl, Ca, inorganic phosphorus, urea nitrogen, creatinine, uric acid, total bilirubin, direct bilirubin, ALT, AST, $\gamma$ -GTP, ALP, LDH, CK, amylase, total cholesterol, triglycerides, LDL-C, HDL-C, total protein, albumin, glucose
Coagulation test	Prothrombin time, activated partial thromboplastin time
Urinalysis	Qualitative tests (pH, specific gravity, protein, glucose, occult blood, urobilinogen, bilirubin, ketones)

Any BLQ data will be treated as 0 in summary statistics.

**7.10.3 Vital Signs**

All vital sign data will be listed.

Vital signs (systolic blood pressure, diastolic blood pressure, pulse rate, body temperature) values and changes from baseline will be summarised descriptively by cohort, group and scheduled time point.

#### 7.10.4 12-lead ECGs

All 12-lead ECG parameters and findings (Heart Rate, RR, PR, QRS, QT, QTcF, overall evaluation) will be listed. 12-lead ECG parameter values and changes from baseline will be summarized descriptively by cohort, group and scheduled time point.

For ECGs, number and percentage of subjects meeting the criteria listed below will be presented:

- $QTcF > 500\text{msec}$  at timepoint
- $500 \geq QTcF > 480\text{msec}$  at timepoint
- $480 \geq QTcF > 450\text{msec}$  at timepoint
- $QTcF \leq 450\text{msec}$  at timepoint
- Change from baseline in  $QTcF > 30\text{ msec}$
- Change from baseline in  $QTcF > 60\text{ msec}$

A listing of 12-lead ECG parameter values will be provided for subjects with any clinical significant findings.

#### 7.10.5 Sensory Tests

All sensory tests data will be listed.

Sensory tests (vibratory sensation) values and changes from baseline will be summarized descriptively by group and by visit.

With respect to sensory tests (numbness and staggering) including severity, a shift table of the changes from baseline will be shown by group and by visit.

#### 7.10.6 Physical Examinations

All physical examination data will be listed.

### 8. CHANGES FROM THE PROTOCOL

The definition of PKPOP and SAF is changed from the protocol. The reason to change the definition of SAF is to enable assessments of safety of any administration regardless of study drug.

The reason to change the definition of PKPOP is to enable assessments of effect on pharmacokinetics of victim drugs by edaravone using subjects whose PK data are available regardless of completion of all treatments (victim drug alone and victim drug + edaravone).

## **9. DATA NOT SUMMARISED OR PRESENTED**

Not applicable in the study.

## **11. VALIDATIONS**

SAS software version 9.4 or later will be used for statistical analysis.

Phoenix WinNonlin (release 6.3 or a later version) will be used to calculate Pharmacokinetics Parameters.

## **12. PROGRAMMING AND DATA PRESENTATION CONVENTIONS**

### **12.1 For Summary Statistics and Safety**

- Minimum and maximum will be quoted to the number of decimal places (DP) as recorded for the original (observed) data.
- Means, medians and SD will be quoted to one further DP.

### **12.2 For Plasma Concentrations**

- Individual values, minimum and maximum will be presented with the number of decimal places to which they are reported,
- Summary statistics (mean, SD, median and geometric mean) will be presented with 2 DPs for edaravone and its metabolites, and each victim drug.
- Summary statistics (CV% and geometric mean CV %) will be presented to 1 DP.
- Individual values and summary statistics for ratio of trough concentrations will be presented to 3 DPs.

### **12.3 For PK Parameters**

- Individual values and summary statistics will be presented with a number of decimal places as shown in the table below.
- Ratios of geometric LS means and CIs will be presented as percentages. Percentages will be presented to two DPs.

**Number of Decimal Places for the Presentations of PK Parameters**

Statistics	Unit	Individual value, Minimum, Maximum	Mean, SD, Geometric mean	CV%, Geometric CV %
AUC	h·ng/mL	2	2	1
C max	ng/mL	Reported value	2	1
t max	h	2	2	1
Kel	1/h	5	5	1
t 1/2	h	2	2	1
Vz/F	L	0	0	1
CL/F	L/h	0	0	1
MRT	h	2	2	1
Number of Kel points	—	0	—	—
Lower Limit of Kel	h	2	—	—
Upper Limit of Kel	h	2	—	—
Adjusted R 	—	2	—	—
AUC% ex	%	2	—	—

AUCs ratio and Cmax ratio will be presented to 3 DPs.

#### 12.4 Other Specifications

- Column headers in mixed case, with “(N=n)” below period to denote the denominator.
- Categories (i.e. in column 1) in sentence case, in the order on the CRF.
- Ordering of statistics N, Mean, SD, Minimum, Median and Maximum (and labelled as such). CV%, geometric means and geometric CV% also for PK parameters.

### 13. PHARMACOKINETIC PARAMETER CALCULATIONS

- Actual blood sampling times for the assay of edaravone and its metabolites, rosuvastatin, sildenafil, and furosemide will be used in the calculation of pharmacokinetic parameters
- All concentrations below the LLOQ will be set at zero for pharmacokinetic calculations
- When Kel is missing (or cannot be determined),  $t_{1/2}$ ,  $AUC_{0-\infty}$ , MRT, CL/F and  $V_z/F$ ,  $V_{ss}/F$  will not be calculated.

PK Parameter Calculations		
Parameters	Unit	Calculation
$AUC_{0-t}$	h·ng/mL	will be calculated using the linear trapezoidal method and actual times $AUC_{0-t} = \sum_{i=1}^n \frac{t_i - t_{i-1}}{2} (C_{i-1} + C_i)$
$AUC_{0-24}$	h·ng/mL	will be calculated using time until 24 h drug concentration
$AUC_{0-\infty}$	h·ng/mL	$AUC_{0-\infty} = AUC_{0-t} + \frac{C_{last}}{Kel}$
$C_{max}$	ng/mL	will be determined using maximum drug concentration
$t_{max}$	h	will be determined using time to maximum drug concentration
$t_{1/2}$	h	$t_{1/2}$ will be determined as: $t_{1/2} = \frac{\log_e(2)}{Kel}$
Kel	1/h	
The exponential rate constant of the terminal phase, kel, will be estimated by log-linear regression, if determinable. The number of data points included in the regression will be determined by visual inspection. Wherever possible, a minimum of 3 data points will be used in the estimation of Kel.
 
During the analysis, this calculation method repeats regressions using the last three points with non-zero concentrations, then the last four points, last five, etc. The time of maximum concentration (tmax) will be excluded from the estimation of Kel.
 
Points with a value of zero for the dependent variable are excluded. For each regression, an adjusted <math>R^2</math> is computed
 $\text{Adjusted } R^2 = 1 - \frac{(1 - R^2) + (n - 1)}{(n - 2)}$ 
where n is the number of data points in the regression and <math>R^2</math> is the square of the correlation coefficient.
 
The regression with the largest adjusted <math>R^2</math> is selected to estimate kel, with these caveats:
 
 
- If the adjusted <math>R^2</math> does not improve, but is within
 

		
0.0001 of the largest adjusted <math>R^2</math> value, the regression with the larger number of points is used.
 
 
- kel must be positive, and calculated from at least three data points.
 

MRT	h	$AUMC_{0-\infty} = \sum_{i=1}^n \frac{(t_i - t_{i-1})(t_i \times C_i + t_{i-1} \times C_{i-1})}{2} + \frac{t \times C_t}{K_{el}} + \frac{C_t}{(K_{el})^2}$ $MRT_{0-\infty} = \frac{AUMC_{0-\infty}}{AUC_{0-\infty}}$
CL/F	L/h	$CL/F = \frac{Dose}{AUC_{0-\infty}}$
$V_z/F$	L	$V_z/F = CL/F \times \frac{1}{K_{el}}$
$V_{ss}/F$	L	$V_{ss}/F = MRT \times CL/F$
Number of Kel points	—	will be determined using number of points used in computing Kel. If Kel cannot be estimated, zero.
Lower Limit of Kel	h	will be determined using lower limit on time to be included in the calculation of Kel
Upper Limit of Kel	h	will be determined using upper limit on time to be included in the calculation of Kel
AUC% ex	—	$AUC\%_{ex} = \frac{AUC_{0-\infty} - AUC_{0-t}}{AUC_{0-\infty}} \times 100$

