5.2.1.3 Study Period and Evaluation Period

Study period: The study period is defined as the period from informed consent to completion of the end-of-study assessment (or to completion or termination of follow-up, for any followed-up subjects).

Screening: Subjects providing informed consent will be screened for eligibility to select subjects meeting all of the inclusion criteria and none of the exclusion criteria (Cohort 1: 66 subjects [32 for Group 1 and 34 for Group 2], with a few reserve subjects; Cohort 2: 9 Japanese and 9 Caucasian subjects with a few reserve subjects).

Evaluation period: Cohort 1: The evaluation period is defined as the period from completion of dosing of the study drug or victim drugs (rosuvastatin, sildenafil, and furosemide) on Day 1 to completion of the end-of-study assessment. The duration of hospitalization will be 16 days and 15 nights (Day -1 to Day 15) for Group 1, and 10 days and 9 nights (Day -1 to Day 9) for Group 2.
Cohort 2: The duration of hospitalization will be 10 days and 9 nights (Day -1 to Day 9) for Japanese subjects, and 4 days and 3 nights (Period I, Day -1 to Day 3; Period II, Day 3 to Day 6; Period III, Day 6 to Day 9) for Caucasian subjects.

End-of-study assessment: The prespecified observations and tests will be performed as the end-of-study assessment, 7 days (\pm 2 days) after the last dose of the study drug.

[Rationales for setting]

(1) Cohort 1

In this study, drug interactions will be assessed for enzymes and transporters specified in FDA's DDI (drug-drug interactions) Draft Guidance 2017 as requiring DDI assessment.

An open-label, add-on study has been considered appropriate because the objective of this cohort is to evaluate the effects of drug-drug interactions on pharmacokinetics. Drug interactions will be assessed between the perpetrator drug in a steady state reached by multiple doses of it and the victim drugs. This assessment will be performed based on PK parameter changes obtained by single doses of the victim drugs.

Group 1: When edaravone was incubated with human hepatocytes for 48 hours, edaravone increased mRNA expression of CYP3A at high concentration, which indicated that edaravone had induced CYP3A4 at high concentration. This finding suggests that oral edaravone may cause drug interactions with CYP3A4 substrates by inducing CYP3A4 in intestinal epithelial cells. Moreover, edaravone showed its inhibitory effect on the BCRP transport activity, with IC₅₀ of 121

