#### **3.3 Pharmacokinetics Endpoint(s)/Evaluation(s)**

The pharmacokinetic parameters in plasma will be determined from the individual concentration vs. time data by non-compartmental analysis using WinNonlin® professional version 6.3 or later. The exact sampling time (in hours rounded to 3 decimal places) relative to dosing will be used in calculation. For the calculation of PK parameters concentration below the limit of quantification (BLQ) will be imputed with a value of zero.

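### SAP 13 applies single-dose clearance formulas to repeat-dose edaravone profiles, biasing CL/F low, probably by a few percent; its Kel rule and printed adjusted R-squared also need tidying

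*SAP*

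**What the plan says.** **Clearance and volumes.** SAP 13 gives one set of formulas for all profiles: CL/F = Dose/AUC0-inf, Vz/F = (CL/F)/Kel, MRT = AUMC0-inf/AUC0-inf and Vss/F = MRT × CL/F. There is no repeat-dose version. SAP 7.9.2 requires these for unchanged edaravone, given alone and with each victim drug, and summarises them by treatment. Protocol 5.2.1.3 describes the state in which the combination is studied: "Drug interactions will be assessed between the perpetrator drug in a steady state reached by multiple doses of it and the victim drugs".

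**Kel.** In the Kel row, SAP 13 says "The number of data points included in the regression will be determined by visual inspection". The same cell continues with an automatic search: "this calculation method repeats regressions using the last three points with non-zero concentrations, then the last four points, last five, etc". The regression with the largest adjusted R-squared "is selected to estimate kel, with these caveats". The minimum number of points also appears in two forms: "Wherever possible, a minimum of 3 data points will be used in the estimation of Kel" and "kel must be positive, and calculated from at least three data points". The printed adjusted R-squared adds (1 − R²) and (n − 1) where the usual expression multiplies them.

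**Software.** SAP 3.3 specifies "non-compartmental analysis using WinNonlin® professional version 6.3 or later".

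**The concern.** On a repeat-dose day, the area extrapolated to infinity contains drug from earlier doses as well as the current one. Dividing a single dose by that area understates clearance. Edaravone alone is profiled after its first dose, and edaravone with a victim drug after its 4th or 7th. The error therefore falls on one side of the comparison only. A reader could take the resulting difference as a small effect of the victim drug on edaravone, whose pharmacokinetics are a secondary objective of Cohort 1.

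The Kel text raises a separate question of reproducibility. Two analysts could follow different sentences of the same cell and choose different points. The printed adjusted R-squared, if used as it stands, would not rank the regressions sensibly.

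**Working it through.** The documents give no value for Kel, half-life, CL/F or volume, so there is no plan figure to reproduce. The check works from the formulas.

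**1. Which profiles are affected.** Group 1 receives edaravone on Days 6 to 13 and Group 2 on Days 3 to 7 (Protocol 8.4). Full edaravone profiles are taken on Days 6, 9 and 12, and on Days 3 and 6 (Protocol 9.2.4.1). Days 6 and 3 are first doses. Days 9 and 12 are the 4th and 7th doses in Group 1; Day 6 is the 4th in Group 2. The next day's pre-dose sample supplies the 24 h point, so AUC0-24 is available for each. Victim drugs and Cohort 2 are assessed as single doses.

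**2. Upper bound on the CL/F bias.** The input is the terminal half-life of 5.1 to 11.8 h (Protocol 1(3), read as the suspension). In a one-compartment model with a 24 h interval, let x = 2^(−24/t½). After dose N the profile is scaled by S = (1 − x^N)/(1 − x), and Dose/AUC0-inf equals the true CL/F divided by S.

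- t½ = 5.1 h: x = 0.0383, S = 1.040 at N = 4 and 7; bias 1/1.040 − 1 = −3.8%.
- t½ = 8 h (assumed mid-value): x = 0.125, S = 1.143; bias −12.5%.
- t½ = 11.8 h: x = 0.2442, S = 1.318 (N = 4) and 1.323 (N = 7); bias about −24%.

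In the same model Dose/AUC0-24 is within 0.4% of the true value in every case.

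**3. More realistic size.** The bound puts all exposure in the terminal phase. If only a fraction f of AUC lies there and the faster phases do not carry over, the bias is 1/(1 − f + f·S) − 1. The documents do not give f, so 5% to 30% is assumed.

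- t½ = 5.1 h: −0.2% to −1.2%.
- t½ = 8 h, f = 0.20: 1/(0.80 + 0.20 × 1.143) − 1 = −2.8%.
- t½ = 11.8 h: −1.6% to −8.8%.

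Vz/F carries the same proportional bias at a given Kel. With several phases, carry-over weights the slow phase more, so MRT lengthens while CL/F falls. These pull Vss/F in opposite directions, and its net error is not determined here.

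**4. Adjusted R-squared as printed.**
1 − [(1 − R²) + (n − 1)]/(n − 2) = (R² − 2)/(n − 2).

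This is negative for every R². At R² = 0.90 it gives −1.10, −0.55 and −0.367 for n = 3, 4 and 5. The standard 1 − (1 − R²)(n − 1)/(n − 2) gives 0.800, 0.850 and 0.867. As printed, a fit on n + 1 points beats a perfect fit on n points once its R² exceeds (n − 3)/(n − 2): 0.50 for n = 4, 0.80 for n = 7.

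**5. What it would do if followed literally.** Simulation: 2,000 profiles per case at the Cohort 1 edaravone times. The curves are assumed: three phases with half-lives 0.35 h, 1.5 h and the terminal value, 8% noise and an assumed quantification cut-off.

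| Terminal t½ (h) | Median points, printed / standard | Median t½ (h), printed / standard | Vz/F ratio | CL/F ratio |
|---|---|---|---|---|
| 5.1 | 8 / 3 | 1.6 / 2.4 | 0.70 | 1.004 |
| 8 | 9 / 3 | 3.0 / 5.8 | 0.53 | 1.006 |
| 11.8 | 9 / 3 | 3.4 / 7.9 | 0.45 | 1.019 |

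Ratios are printed over standard. The printed form chose the longest regression in every profile. The standard form also falls short of the true terminal half-life with these curves, so the table compares the two rules and does not validate either. For victim-drug-like curves (assumed terminal half-lives 3, 4 and 18 h, sampling to 48 h), AUC0-inf fell by 0.1% to 3.1%.

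**The case against.** The strongest reply is that these are descriptive parameters and the software will do the work. Much of that stands.

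- A reader might infer that half-life and volumes will come out wrong. The documents do not show this. Parameters are computed in WinNonlin, and nothing says the printed expression will be coded. The plus sign may be a typing error or a fault in reading the PDF. Adjusted R-squared is listed for each profile with a Kel, so negative values throughout would be noticed.
- A reader might infer that the no-effect conclusion is at risk because it rests on AUC0-inf, which needs Kel. That conclusion concerns victim drugs given as single doses. Cmax does not use Kel, the same rule serves both treatments, and AUC0-inf moved by at most about 3% in the assumed curves. AUC0-t and AUC0-24 are fitted alongside with 90% CIs, though they do not enter the decision.
- A reader might take 24% as the expected bias. That end assumes one compartment. Protocol 1(3) reports decline in several phases and no accumulation over five days, which point to the low end.
- A reader might extend the point to the metabolites. CL/F, MRT and volumes are derived only for unchanged edaravone.
- Visual selection is not hidden: the number of points, their time limits and the extrapolated percentage are all listed. The listing does not give the reason for a choice or say which rule prevails.

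The reply does not answer the repeat-dose formula. It is the wrong definition for those days whatever the software or the PDF reading.

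**Conclusion.** The point holds in a limited form. CL/F, and Vz/F with it, for unchanged edaravone on Days 9 and 12 (Group 1) and Day 6 (Group 2) will be biased low against edaravone alone. The bound is about 4% to 24%; a few percent is more likely. The bound rests on the reported half-life range and one-compartment superposition with constant clearance; the lower figures rest on an assumed 5% to 30% terminal share of AUC. The comparison affected is descriptive, with no test or confidence interval planned.

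The Kel text has two point-selection rules with no stated precedence, and a printed adjusted R-squared that cannot be right as it reads. If followed literally it would raise Kel and cut half-life and Vz/F substantially, with little effect on CL/F or AUC0-inf. Whether it would be followed is not known. The Cohort 1 no-effect decision is unlikely to change.

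**What to change.** 1. For edaravone on Days 9 and 12 (Group 1) and Day 6 (Group 2), define CL/F as Dose/AUC0-24 and base Vz/F on that CL/F. AUC0-24 is already derived, and Protocol 10.1 leaves calculation details to the SAP.
2. On those days, either flag AUC0-inf, MRT and Vss/F as not interpretable as single-dose values, or omit them. Protocol 5.4.2 and 10.1 list them for edaravone in combination, so omission departs from the protocol. Record the change and its reason in SAP 8 and, as Protocol 13.5 requires, in the study report. Flagging avoids the departure.
3. Check the operator in the source file and print adjusted R² = 1 − (1 − R²)(n − 1)/(n − 2).
4. State that the automatic best-fit rule governs Kel, keep the mandatory three-point minimum, and list any visual override with its reason.

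The cost is SAP wording and a small change to the edaravone parameter programming and footnotes. No new samples or data are needed.
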